8.8.2 Methods to derive parameters of interest

Calendar time

Calendar time will be based on the calendar year of the index prescription.

Age

Age at index date will be calculated using January 1st of the year of birth as a proxy for the actual birthday. Age will be presented as a mean/median age as well as proportion of patient stratified within age groups (<18, 18-44, 45-64, 65-79, and ≥ 80).

Sex

Results will be presented stratified by sex (men/women).

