7. RESEARCH QUESTION AND OBJECTIVES

The aim of this study is to characterise individuals treated with Azathioprine.

The specific study objectives are:

1. Characterise azathioprine initiators by sex and age at first prescription, overall and per indication
2. Identify potential indications for azathioprine, and the percentage of azathioprine-treated patients for each pre-defined approved indication:
 - a) Organ transplantation
 - b) Severe rheumatoid arthritis or chronic polyarthritis
 - c) Inflammatory bowel disease
 - d) Autoimmune hepatitis
 - e) Systemic lupus erythematosus
 - f) Dermatomyositis
 - g) Polyarteritis nodosa
 - h) Pemphigus vulgaris and bullous pemphigoid
 - i) Behçet's disease
 - j) Refractory autoimmune haemolytic anaemia
 - k) Refractory idiopathic thrombocytopenic purpura
 - l) Polymyositis
 - m) Pyoderma gangrenosum
 - n) Multiple sclerosis
 - o) Myasthenia gravis
 - p) None of the above/missing
3. Large-scale characterisation overall and per indication of drugs and conditions within one year prior to the index date (-365 to -1 day to the index date) and on the index date will be assessed.
4. Estimate and summarise duration of treatment with azathioprine, overall, and stratified per indication

Description of the proposed objectives are described in ([Table 1](#)).

Table 1. Primary and secondary research questions and objective.

A. Primary research question and objective.

Objective 1,2,3 and 4:	To characterise individuals newly treated with Azathioprine by age and sex. In addition, new users of Azathioprine will be characterised in terms of indication and treatment of use. Characterisation will be done in terms of demographics, indication, treatment duration and prior drug use and comorbidities
Hypothesis:	N/A
Population (mention key inclusion-exclusion criteria):	All patients present in the databases with at least 365 days of prior history and newly treated with Azathioprine
Exposure:	Exposure to Azathioprine

	D2.2.3 - Study Protocol for P3-C1-014	
	Author(s): [name], [name]	Version: V4.0
	Dissemination level: Public	

Comparator:	N/A
Outcome:	N/A

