8.6.3 Other covariates, including confounders, effect modifiers and other variables

The study covariates are described conceptually, and the context or rationale for the choices are provided in this section. The operational definition of the covariates is described in the [Table 9](#).

Covariates for the patient-level characterisation

To characterise the new initiators of Azathioprine, the covariates will include:

- age at the index date (first prescription of Azathioprine) presented as a mean/median age as well as proportion of patient stratified within age groups (<18, 18-44, 45-64, 65-79, and >=80), overall and per indication
- sex (male/ female), overall and per indication.
- Conditions considered indications for Azathioprine use, will be assessed within -90/+30 days of the index date. These indications will be identified based on the presence of disease codes. The preliminary code list for each condition of interest is available in [Appendix I](#).

Indications:

- Organ transplantation
- Severe rheumatoid arthritis or chronic polyarthritis
- Inflammatory bowel diseases
- Autoimmune hepatitis
- Systemic lupus erythematosus
- Dermatomyositis
- Polyarteritis nodosa
- Pemphigus vulgaris and bullous pemphigoid
- Behcet's disease
- Refractory autoimmune haemolytic anaemia
- Refractory idiopathic thrombocytopenic purpura
- Polymyositis

	D2.2.3 - Study Protocol for P3-C1-014	
	Author(s): [name], [name]	Version: V4.0
		Dissemination level: Public

- Pyoderma gangrenosum
 - Multiple sclerosis
 - Myasthenia gravis
 - None of the above/missing
- Large-scale characterisation: overall and per indication of drugs (by RxNorm code at ingredient level) and conditions (by standard SNOMED code) within one year prior to the index date (-365 to -1 day to the index date) and at the index date will be assessed. While all conditions and medications above 1% will be available within the Shiny App, only the 10 most frequent conditions and drugs will be described within the report. Drugs will be reported by ingredient and not by strength or formulation

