8.8.4 Output

New drug user, patient-level characterisation:

- Table 1. Study attrition of individuals included in each cohort per database.
- Table 2. Number and proportion of participants treated with azathioprine. Distribution (number and %) overall and stratified by sex, age and age-groups Number of participants per pre-specified strata will be included where necessary/applicable.
- Table 3. Distribution of prespecified indications in participants with azathioprine. Number of participants per pre-specified strata will be included where necessary/applicable.
- Table 4. Large-scale characterisation: top 10 drugs (ingredient level) in the year prior to index date ([-365, -1]).
- Table 5. Large-scale characterisation: top 10 conditions in the year prior to index date ([-365, -1]).
- Table 6. Large-scale characterisation: top 10 drugs (ingredient level) on index date ([0,0]).
- Table 7. Large-scale characterisation: top 10 conditions on index date ([0,0]).
- Table 8: Duration of treatment for Azathioprine overall and per prespecified indication. Proportion (%) of patients with a duration that fall within the prespecified treatment duration group (<12 months, 12-24 months, 2-3 years, 3-4 years, 4-5 years, 5-10 years and ≥10 years.), both overall and per indication.

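### Taking 1 January of the birth year as everyone's birthday biases age upward by about half a year and under-counts initiators below 18; a mid-year proxy nearly removes both errors

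*Protocol*

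**What the plan says.** Protocol section 8.8.2 fixes the rule for deriving age: "Age at index date will be calculated using January 1st of the year of birth as a proxy for the actual birthday". It allows no exception and gives no reason for choosing 1 January over another date.

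The derived age is used in three places:
- Objective 1 (section 7): "Characterise azathioprine initiators by sex and age at first prescription, overall and per indication".
- Section 8.6.3, which asks for mean and median age and for the "proportion of patient stratified within age groups (<18, 18-44, 45-64, 65-79, and >=80" years, overall and per indication.
- Output Table 2 (section 8.8.4): "Distribution (number and %) overall and stratified by sex, age and age-groups".

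Section 11 (limitations) says in which direction treatment duration may be wrong. It says nothing about error in age.

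**The concern.** A proxy birthday is reasonable when only the birth year is used, but its position within the year decides whether the error has a direction. 1 January puts all of the error on one side. A larger cohort does not average it out. The same rule applies in all five databases, so setting their results side by side will not reveal it.

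Age at initiation is one of the few things this study is meant to deliver. Section 6 names the age distribution among the information that will support the signal evaluation. The group most exposed is the under-18 group, which can lose patients across its upper boundary but has no lower boundary across which to gain any. In small indication strata, losing a few minors could also bring a cell below 5, where section 8.8 suppresses it.

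**Working it through.** The protocol states no figure for the error in age, so there is none to reproduce. The size follows from the rule itself.

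**Inputs.** From the protocol: birthday set to 1 January (8.8.2); cut-points at 18, 45, 65 and 80 (8.6.3). Assumed: birthdays and index dates spread evenly over the year. Let *u* be the fraction of the birth year elapsed at the true birthday, and *f* the fraction of a year lived since the last birthday at index, both uniform on (0,1) and independent.

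**1. Mean error with 1 January.** Derived minus true exact age = *u*. It lies between 0 and just under 1 year, with mean E[*u*] = 0.5 year.

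In completed years, derived age is one year too high when *f* + *u* ≥ 1, which has probability 0.5; otherwise it is correct. The mean error is again 0.5 year. A day count agrees: on day *k* of a 365-day year (*k* = 0 on 1 January), 364 − *k* of the 365 possible birthdays are still to come. The average over *k* is 182/365 = 0.4986.

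**2. Crossing at 18.** A true 17-year-old is placed in 18-44 when *f* + *u* ≥ 1, so the probability is 0.5. No true 18-year-old moves down, because the error is never negative. The 0.5 is an average over index dates. At year fraction *t* it is about 1 − *t*: for 15 January, 1 − 14/365 = 96%; for 15 December, 1 − 348/365 = 5%.

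**3. Shortfall in the under-18 group.** The shortfall is 0.5 × (share of 17-year-olds among minors). With a flat age distribution starting at age *a*, this is 0.5/(18 − *a*):

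| Assumed ages of minors | Shortfall |
|---|---|
| 0-17 | 0.5/18 = 2.8% |
| 10-17 | 0.5/8 = 6.3% |
| 12-17 | 0.5/6 = 8.3% |
| 14-17 | 0.5/4 = 12.5% |

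For scale, an assumed true under-18 share of 4% would be reported as 4% × (1 − 0.028) = 3.9% in the first case and 4% × (1 − 0.083) = 3.7% in the third.

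**4. Other groups.** The 18-44 group gains half of the 17-year-olds and loses half of the 44-year-olds. The groups 45-64 and 65-79 behave the same way, each with a net change of half the difference between two single-year counts. The group aged 80 and over gains half of the 79-year-olds and loses nobody.

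**5. Mid-year proxy.** With 1 July the error in exact age is *u* − 0.5, with mean 0.
- A 17-year-old moves up when *f* + *u* ≥ 1.5: probability 0.5 × 0.5 × 0.5 = 12.5%.
- An 18-year-old moves down when *f* + *u* < 0.5: also 12.5%.
- Day-by-day enumeration over one calendar year gives 12.6% and 12.4%.

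The share of patients with a wrong completed age falls from 50% to 12.5% + 12.5% = 25%. The net change at 18 is 0.125 × (number aged 18 − number aged 17). If, for illustration, 18-year-olds were 20% more numerous, the under-18 group would gain 0.125 × 1.2 − 0.125 = 2.5% of the 17-year-old count. Under 1 January it loses 50% of that count.

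**The case against.** The strongest objection is that the half-year bias depends on the quantity being estimated. Under the 1 January rule, whole-year age is index year minus birth year. With even spread, its mean equals the mean *exact* age, because completed age lies on average half a year below exact age. The protocol does not say whether age is kept in completed years or as a decimal; Table 9 lists demographics only as numeric, continuous and binary. This stands as a limit on the wording: the +0.5 year applies when like is compared with like. It does not touch the age groups, which are defined by completed years whichever way age is stored.

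A second objection is that a single rule run locally in every database is worth keeping. That is right, and 1 July keeps it, since it too needs only the birth year. Nor is 1 July error-free: it makes some ages too low and still gets a quarter of completed ages wrong.

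A third is that the consequence is slight. The study is descriptive, tests no hypothesis, has no eligibility rule based on age, and states the proxy openly in 8.8.2. All true, and this keeps the point minor. But stating the proxy is not the same as telling readers which way it pushes the results.

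**Conclusion.** The point holds as a minor, systematic bias. Given even spread of birthdays and index dates, mean age is about 0.5 year too high like for like, about half of true 17-year-olds are counted as adults with no return flow, and the under-18 group is short by roughly 3% to 12.5%. Within that range the size depends on a paediatric age mix that the protocol does not give; the direction does not.

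A reader might infer more than the protocol supports:
- *Every patient is half a year too old.* The half year is a mean. Error in exact age runs from 0 to just under 1 year, and in completed years about half of patients are correct.
- *Every age group loses patients.* Only the under-18 group loses without gaining. The group aged 80 and over only gains, and the middle groups do both.
- *The shortfall in minors is near the top of the range.* That would need 17-year-olds to make up about a quarter of minors, for which there is no evidence in the protocol.
- *Known birthdays are being discarded.* The protocol does not say that any of the five databases holds day or month of birth.

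A shift of this size in adult mean age is unlikely to alter the signal evaluation.

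**What to change.** In section 8.8.2, replace 1 January with 1 July of the birth year as the single proxy in all five databases. The cost is one sentence in the protocol and one setting in the study code, with no additional data. The small downside is that some ages become too low: about 12.5% of true 18-year-olds would be classed as under 18, nearly offset by the 12.5% of 17-year-olds classed as adults. In the same sentence, say whether age is reported in completed years or as a decimal.

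If 1 January has to stay, add a sentence to section 11 saying that age is biased upward by about half a year on average and that the under-18 group is under-counted.

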8.8.3 Patient-level characteristics on/before index date

Characterisation of patients newly treated with Azathioprine: We will use the R package “PatientsProfiles” for the patient-level characterisation of demographics and predefined clinical characteristics, as well as large-scale characterisation. The co-variables to be presented in a summary baseline characteristics table have been described in section 8.6.3.

Characterisation of treatment with azathioprine in a cohort of new users: The “DrugUtilisation” package will be used to characterise the use of Azathioprine.

The number and % of patients receiving Azathioprine for a prespecified list of indications including duration of treatment.

	D2.2.3 - Study Protocol for P3-C1-014	
	Author(s): [name], [name]	Version: V4.0
		Dissemination level: Public

8.8.4 Output

New drug user, patient-level characterisation:

- Table 1. Study attrition of individuals included in each cohort per database.
- Table 2. Number and proportion of participants treated with azathioprine. Distribution (number and %) overall and stratified by sex, age and age-groups Number of participants per pre-specified strata will be included where necessary/applicable.
- Table 3. Distribution of prespecified indications in participants with azathioprine. Number of participants per pre-specified strata will be included where necessary/applicable.
- Table 4. Large-scale characterisation: top 10 drugs (ingredient level) in the year prior to index date ([-365, -1]).
- Table 5. Large-scale characterisation: top 10 conditions in the year prior to index date ([-365, -1]).
- Table 6. Large-scale characterisation: top 10 drugs (ingredient level) on index date ([0,0]).
- Table 7. Large-scale characterisation: top 10 conditions on index date ([0,0]).
- Table 8: Duration of treatment for Azathioprine overall and per prespecified indication. Proportion (%) of patients with a duration that fall within the prespecified treatment duration group (<12 months, 12-24 months, 2-3 years, 3-4 years, 4-5 years, 5-10 years and ≥10 years.), both overall and per indication.

8.9 Evidence synthesis

Results from analyses described in section 8.8 will be presented separately for each database. No meta-analysis will be conducted.

9. DATA MANAGEMENT

9.1 Data management

All databases are mapped to the OMOP common data model. This enables the use of standardised analytics and tools across the network since the structure of the data and the terminology system is harmonised. The OMOP CDM is developed and maintained by the Observational Health Data Sciences and Informatics (OHDSI) initiative and is described in detail on the wiki page of the CDM:

<https://ohdsi.github.io/CommonDataModel> and in The Book of OHDSI: <http://book.ohdsi.org>.

The analytic code for this study will be written in R. Each data partner will execute the study code against their database containing patient-level data and will then return the results set which will only contain aggregated data. The results from each of the contributing data sites will then be combined in tables and figures for the study report.

9.2 Data storage and protection

For this study, participants from various EU member states will process personal data from individuals which is collected in national/regional electronic health record databases. Due to the sensitive nature of this personal medical data, it is important to be fully aware of ethical and regulatory aspects and to strive to take all reasonable measures to ensure compliance with ethical and regulatory issues on privacy.

	D2.2.3 - Study Protocol for P3-C1-014	
	Author(s): [name], [name]	Version: V4.0
		Dissemination level: Public

All databases used in this study are already used for pharmaco-epidemiological research and have a well-developed mechanism to ensure that European and local regulations dealing with ethical use of the data and adequate privacy control are adhered to. In agreement with these regulations, rather than combining person level data and performing only a central analysis, local analyses will be run, which generate non-identifiable aggregate summary results.

The output files are stored in the DARWIN Digital Research Environment (DRE). These output files do not contain any data that allow identification of subjects included in the study. The DRE implements further security measures in order to ensure a high level of stored data protection to comply with the local implementation of the General Data Protection Regulation (GDPR) (EU) 679/20161 in the various member states.

10. QUALITY CONTROL

General database quality control

A number of open-source quality control mechanisms for the OMOP CDM have been developed (see Chapter 15 of The Book of OHDSI <http://book.ohdsi.org/DataQuality.html>). In particular, data partners have run the OHDSI Data Quality Dashboard tool (<https://github.com/OHDSI/DataQualityDashboard>). This tool provides numerous checks relating to the conformance, completeness and plausibility of the mapped data. Conformance focuses on checks that describe the compliance of the representation of data against internal or external formatting, relational, or computational definitions, completeness in the sense of data quality is solely focused on quantifying missingness, or the absence of data, while plausibility seeks to determine the believability or truthfulness of data values. Each of these categories has one or more subcategories and are evaluated in two contexts: validation and verification. Validation relates to how well data align with external benchmarks with expectations derived from known true standards, while verification relates to how well data conform to local knowledge, metadata descriptions, and system assumptions.

Study specific quality control

When defining specific drugs, conditions, and co-morbidities, a systematic search of possible codes for inclusion was previously identified using CodelistGenerator R package (<https://github.com/darwin-eu/CodelistGenerator>). This software allows the user to define a search strategy and, using this will then query the vocabulary tables of the OMOP CDM to find potentially relevant codes. The codes returned will then be reviewed by two clinical epidemiologists to consider their relevance. In addition, the CohortDiagnostics R package (<https://github.com/OHDSI/CohortDiagnostics>) will be run to assess the use of different codes across the databases contributing to the study and identify any codes potentially omitted in error. This will allow for a consideration of the validity of the study cohort of patients with the selected conditions, drugs, and co-morbidities in each of the databases and inform decisions around whether multiple definitions are required.

11. LIMITATIONS OF THE RESEARCH METHODS

Regarding azathioprine use, the recording of the prescription of the drug (e.g. concept id at clinical drug level or at ingredient level), and the prescriptions themselves may vary across databases. In addition, a recording of a prescription or dispensation does not mean that the patient actually took the drug. In addition, assumptions around the duration of drug use will be unavoidable and might lead to overestimating treatment duration of treatment (considering a 30-day drug gap era).

	D2.2.3 - Study Protocol for P3-C1-014	
	Author(s): [name], [name]	Version: V4.0
		Dissemination level: Public

For this study, the indication of use is important and predefined indications of use have been identified. Not all of these indications of interest might be present within the database (i.e. in DP with less granular source coding such as IPCI). For that reason, it might be interesting to use more broad definitions of the indication of use (e.g. look for “inflammatory disease of liver” and not necessarily “autoimmune hepatitis”. These broad searches might impose a potential of misclassification however, as we search in a relatively small window, 3 months before and 1 month after, around the index date (first prescription of azathioprine during study period) this risk of misclassification is probably minimal. Also, the large-scale characterisation (looking for top 10 disease codes) might provide insight into the indication of use on top of the indications which have been predefined.

The study period is from 2000 until 2023 however not all DPs have that long observation time. For IPCI, observation period starts from 2008 and for SIDIAP from 2005.

Small cell counts may affect the analysis for some subgroup strata. If the numbers are too low, counts will not be disclosed for governance reasons.

12. MANAGEMENT AND REPORTING OF ADVERSE EVENTS/ADVERSE REACTIONS

Adverse events/adverse reactions will not be collected or analysed as part of this evaluation. The nature of this non-interventional evaluation, through the use of secondary data, does not fulfil the criteria for reporting adverse events, according to module VI, VI.C.1.2.1.2 of the Good Pharmacovigilance Practices (https://www.ema.europa.eu/en/documents/regulatory-procedural-guideline/guideline-good-pharmacovigilance-practices-gvp-module-vi-collection-management-submission-reports_en.pdf).

Only in case of prospective data collection, there is a need to describe the procedures for the collection, management and reporting of individual cases of adverse events/adverse reactions.

13. GOVERNANCE BOARD ASPECTS

All data sources require approval from their respective IRB boards, except IQVIA DA Germany, which will not require any further specific approvals to undertake this study.

14. PLANS FOR DISSEMINATING AND COMMUNICATING STUDY RESULTS

14.1 Study Report

A PDF report, including an executive summary and the specified tables and/or figures, will be submitted to EMA by the DARWIN EU® CC upon completion of the study.

An interactive dashboard incorporating all the results (tables and figures) will be provided alongside the PDF report. The full set of underlying aggregated data used in the dashboard will also be made available if requested.

	D2.2.3 - Study Protocol for P3-C1-014	
	Author(s): [name], [name]	Version: V4.0
	Dissemination level: Public	

15. OTHER ASPECTS

None.

17. ANNEXES

Appendix I: List of Stand-Alone documents (e.g. lists with concept definitions (conditions & drugs), validation procedures, questionnaires etc.).

